## 11.2. PROCEDURE

General surgery or procedure received will be listed in listings. See [Appendix 1](#) for the handling of partial dates for procedure.

## 12. Study Medication Exposure

### 12.1. STUDY DRUG ADMINISTRATION

Duration of exposure to study drug in weeks from Day 1, number of patients completed for each administration visit, number of administrations, cumulative dose (mg) from Day 1, dose intensity (mg/day) by course, relative dose intensity (RDI) by course, will be summarized by treatment group with descriptive statistics using the SAF. A plot will be prepared to visually present the patient distribution of exposure duration by treatment based on the SAF.

Exposure duration will be calculated according to the following algorithm.

- Exposure duration (weeks) = (last study drug date – first study drug date + 1)/7, Interruptions, compliance, and dose changes are not taken into account for duration of exposure.
- Exposure duration for each course (days) = last infusion date of the course – first infusion date of the course + 1

Dose intensity is derived from the following definitions by course:

- Dose Intensity for 1st course (mg/day) = sum of actual dose administered for the 1st course (mg) / exposure duration for 1st course (days) = sum of actual dose administered for the 1st course (mg) / (last infusion date of the 1st course – first infusion date of the 1st course + 1) (days) .

Dose intensity for 2nd, 3rd and 4th course will follow similar rule as the 1st course above.

RDI is based on the actual dose intensity and the planned dose intensity and will be calculated by course as follows:

- $RDI (\%) = \frac{\text{actual dose intensity}}{\text{planned dose intensity}} \times 100$

Where the planned dose intensity can be calculated following below algorithm:

Planned Dose Intensity for every course (mg/day) = 2000 mg/15 days = 133.3334 mg/day for subjects who completed both infusions in Part A or Part B, and for subjects who only received for the first administration in Part A or Part B, subjects' planned dose intensity will be 1000 mg/1 day = 1000 mg/day.

Administration of study drugs will be listed.

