### **3.12 Treatment Compliance**

The administration (dose, frequency and dates) of all concomitant medications (including new medications taken during the study and investigational product) should be recorded in the appropriate sections of the eCRF from Visit 1.

The infusion schedule consists of two 1,000 mg i.v. drug infusions of either SAIT101 or MabThera® or Rituxan® (the first on Day 1 and the second on Day 15) with the possibility of a further course of two 1,000 mg infusions (see Section 3.2.1). The study drugs will be administered at the study center. This should guarantee that full compliance was achieved, provided the patient attended the appropriate visits. Patients who miss the allocated day for the second of their two infusions will be contacted and another visit arranged as soon as practically possible in order to administer the missed dose of the study drug.

The prescribed dosage, timing, and mode of administration of the study drug may not be changed. Any departures from the intended regimen must be recorded in the eCRF.

Patients exhibiting poor compliance as assessed by attendance to appointments for their drug infusions should be counseled on the importance of good compliance to the study dosing regimen.

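### SAP 12.1 gives a relative dose intensity of 100% to a patient who completed only the first of the two planned infusions

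*SAP*

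**What the plan says.** SAP section 12.1 summarizes dose intensity and RDI by course and treatment group in the Safety Analysis Set. RDI is actual dose intensity over planned dose intensity, times 100. Actual dose intensity is the milligrams given in the course divided by the length of the course in days, and that length is "last infusion date of the course – first infusion date of the course + 1".

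The planned value takes two forms. It is "2000 mg/15 days = 133.3334 mg/day for subjects who completed both infusions in Part A or Part B". But "for subjects who only received for the first administration in Part A or Part B", the "planned dose intensity will be 1000 mg/1 day = 1000 mg/day".

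The protocol has a single plan per course. Section 3.12 states: "The infusion schedule consists of two 1,000 mg i.v. drug infusions", on Day 1 and Day 15, with the possibility of a further course of two. The SAP's modification history records the one-infusion clause as a deliberate addition in draft V1.01. It stands in V2.0, and nothing elsewhere in the SAP overrides it.

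**The concern.** RDI is meant to show how much of the planned treatment was delivered, and at what pace. If the plan is redefined after the fact to equal what the patient got, the ratio cannot register the departure. Missing the second infusion is the largest shortfall possible in a course whose first infusion was completed, and it is the one this rule hides.

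These patients will be in the table. The Safety Analysis Set needs only one dose (SAP 4.4), and the disposition summary in SAP section 8 has a category for patients who completed the first infusion only, in both Part A and Part B. At stake is whether the RDI and dose intensity rows can be read at face value when exposure is compared across arms.

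**Working it through.** **Inputs.** Planned course: two 1,000 mg infusions, Day 1 and Day 15 (Protocol 3.12). Window for the second infusion: Day 15 ± 1 day (Protocol 3.2.2 and Table 2). Longest permitted delay: 15 days, so Day 30 (Protocol 3.2.2). Formulas: SAP 12.1.

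**The plan's own figures.** 2,000/15 = 133.3333 mg/day. The SAP prints 133.3334, a last-digit rounding slip with no practical effect (an on-schedule patient would get 99.99995%). 1,000/1 = 1,000 mg/day, as stated.

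**RDI as written.** Actual intensity = mg given / (last infusion date − first infusion date + 1). RDI = actual / planned × 100.

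| Patient | mg given | Days | Actual (mg/day) | Planned (mg/day) | RDI | Share of 2,000 mg |
|---|---|---|---|---|---|---|
| First infusion only, complete | 1,000 | 1 | 1,000 | 1,000 | 100% | 50% |
| First infusion only, stopped at 500 mg | 500 | 1 | 500 | 1,000 | 50% | 25% |
| Both, second on Day 14 | 2,000 | 14 | 142.86 | 133.33 | 107.1% | 100% |
| Both, second on Day 15 | 2,000 | 15 | 133.33 | 133.33 | 100% | 100% |
| Both, second on Day 16 | 2,000 | 16 | 125.00 | 133.33 | 93.75% | 100% |
| Both, second on Day 30 | 2,000 | 30 | 66.67 | 133.33 | 50% | 100% |

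The patient with one complete infusion ties with the patient dosed exactly on schedule and ranks above the Day 16 patient, who had the full dose inside the window. In the dose intensity row the ratio is 1,000/133.33 = 7.5.

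**Effect on an arm mean (illustration).** Assume an arm of 94, the planned size, with 93 patients fully dosed on Days 1 and 15 and one with a single complete infusion.
- Mean RDI: (93 × 100 + 100)/94 = 100%. The missed infusion leaves no trace.
- Mean dose intensity: (93 × 133.33 + 1,000)/94 = 142.6 mg/day, up 6.9%.
- Mean dose given in the course: (93 × 2,000 + 1,000)/94 = 1,989 mg, down 0.5%.

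Less drug was given, yet mean dose intensity rises.

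**Would changing the denominator alone repair it?** No. With a one-day duration, 1,000/1 over 133.33 gives 750%. Spreading the dose over the planned 15 days gives 1,000/15 = 66.67 mg/day, and 66.67/133.33 = 50%, which agrees with the dose share 1,000/2,000.

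**The case against.** The best defence is that the missed infusion is not hidden from a reader of the report. The same summary in SAP 12.1 gives the number of administrations, the patients completing each administration visit and the cumulative dose, and individual administrations are listed. SAP section 8 counts first-infusion-only patients with reasons. This stands. A reader might infer that the exposure table as a whole cannot show whether exposure was balanced across arms; the documents do not support that.

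Second, a reader might take the values for shifted second infusions (107.1%, 93.75%, 50%) as errors too. They are not. A dose-per-day ratio is meant to fall when the same dose is spread over more days. The Day 16 figure matters only because it exposes the wrong ranking.

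Third, the one-infusion clause was deliberate and avoids the absurd 750%. That explains it but does not justify it: it replaces an obviously wrong value with one that looks right.

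Finally, nothing inferential depends on RDI. The PK and PD sets require both Part A doses, the Per Protocol Set requires both Part A infusions (SAP 4.5 to 4.7), and RDI enters no endpoint, model or equivalence decision. This also stands, and it limits the weight of the point.

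**Conclusion.** The rule is wrong as written, but its reach is small. A patient with one complete infusion gets an RDI of 100% and a dose intensity of 1,000 mg/day after receiving 50% of the planned course. The RDI row therefore cannot reveal a missed second infusion, and dose intensity moves in the wrong direction.

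The 100% rests on that infusion having been given in full; one stopped at 500 mg gives 50%. Likewise, the values for two-infusion patients depend only on timing when both infusions are complete, because a partial infusion lowers the numerator. The number of patients affected is not known from the documents, so the effect on an arm mean can only be illustrated. The conclusion goes no further than two descriptive rows: the primary PK comparison and the main efficacy analysis are untouched.

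**What to change.** Measure every patient who starts a course against the full planned course. Either of two forms will do.

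1. Keep RDI as an intensity. Use 2,000 mg/15 days as the planned value for everyone, and divide a one-infusion patient's actual dose by the planned 15 days. One complete infusion then gives 50%. Both parts must change together. One limit: a full dose with the second infusion on Day 30 also gives 50%, so the row needs reading beside the number of administrations.
2. Report the percentage of planned dose, mg given / 2,000 × 100, for each course started, and tabulate the interval between infusions separately. This drops the time element from the ratio, which is a small loss if the interval is shown.

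Either form also settles a case SAP 12.1 leaves undefined: a second infusion started but not completed, which SAP section 8 expects and which fits neither of the two planned values. For example, 1,500 mg by Day 15 gives 75% under both forms.

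The cost is one formula and its table footnote. No new data are needed, and no dosing rule changes.

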#### Partial date convention

Partial dates will be assumed to be latest possible date of specific visit planned to have study drug infusion, e.g. first infusion of the 2nd course will be assumed as the latest assessment date in Week 24 visit.

---

Document: \\ieedc-vnasc01\Biosdata\Archigen\SAIT101\YWA21301\Biostatistics\Documentation\SAP  
Author: Version Number: V2.0

Version Date: 13Feb2019

Template No: CS\_TP\_BS016 Revision 4  
Effective Date: 01Apr2016

Reference: CS\_WI\_BS005

## 12.2. INFUSION PRE-MEDICATION

'Infusion pre-medication' is either corticosteroids, analgesic or antipyretic, or anti-histamine administered before the start of each study drug infusion.

Administration of infusion pre-medication will be listed in listing.

## 13. Pharmacokinetics Analysis

The PK data collected in Part A and Part B (up through Week 24) will be analyzed according to the treatment administered.

Serum concentrations of rituximab at the time points pre-defined in the study protocol will be measured by a validated method and used for the PK analysis.

Treatment of PK data affected by important protocol deviations and/or events will include the following:

- Randomized study drug not administered or not fully administered, or wrong trial drug administered: In case a dose is not administered or fully administered, any parameters for this subject, if calculated, for this dose and the subsequent dose will not be included in descriptive and/or inferential statistics; the subject will not be part of the PK analysis set per definition. In case of wrong trial drug being administered, patients will be analyzed and included according to the actual treatment they received (rather than the planned treatment), unless there are other additional factors or changes involved that would impact PK.
- Dose is administered outside of the time window provided in protocol (i.e., visit window of  $\pm 1$  day [i.e. 24 hours] for dose on Day 15): Due to the long half-life and extended duration of blood sampling collections, the impact of sampling time deviations on  $AUC_{(0-inf)}$ ,  $AUC_{(0-inf)}$ -related parameters, and  $AUC_{(0-last)}$  would be considered negligible and those parameters will generally not be excluded from descriptive and/or inferential statistics. Similarly,  $C_{max,d2}$  will not be excluded.
- Total duration of infusion not available (i.e., start and/or stop time of infusion missing): Any concentrations or PK parameters based fully or partially on the affected dose will be evaluated at the BDRM.
- Interruption of infusion: Due to the long half-life of the drug, interruptions are expected to have minimal impact on PK parameters that are susceptible to infusion interruptions, as long as the full dose is administered. No parameters will be excluded based on infusion interruptions.
- Pharmacokinetic samples at important phases of the PK disposition curve collected outside the protocol-defined window and/or missing: Important phases include time points around the end-of-infusion, the last sampling time point, and the trough concentration collected prior to dosing on Day 15.
  - End-of-infusion (EOI) and EOI+1h sample Dose 1 and/or 2: If both samples are missing, profiles are not evaluable for AUC and related parameters as well as the affected  $C_{max}/t_{max}$ . If both samples are collected outside of the protocol specified sampling window, data will be assessed during the BDRM to assess whether exclusion of PK parameters is warranted.
  - 336 hours after the 1st dose (i.e., predose second dose on Day 15): See section 13.2 below, for how such deviation at the end of the dosing interval will be treated for calculation of  $AUC_{(0-d15)}$ . In general, if this sample is missing or collected outside of a window of 312 to 360 hours postdose for the 336-hour time point, profiles are not evaluable for  $C_{trough}$ . The impact on  $AUC_{(0-inf)}$ ,  $AUC_{(0-inf)}$ -related parameters, and  $AUC_{(0-last)}$  is considered negligible and those parameters will generally not be excluded from descriptive and/or inferential statistics.
  - Week 24 sample ( $=t_{last}$ ): If the Week 24 sample is missing or is collected outside of the protocol-specified visit window of  $\pm 3$  days,  $AUC_{(0-t)}$  is not evaluable with the exception if the sample prior to the last sample is already BLQ as the missing sample will be inconsequential for profile evaluation.

Document: \\ieedc-vnasc01\Biosdata\Archigen\SAIT101\YWA21301\Biostatistics\Documentation\SAP

Author:

Version Number:

V2.0

Version Date:

13Feb2019

Template No: CS\_TP\_BS016 Revision 4  
Effective Date: 01Apr2016

Reference: CS\_WI\_BS005

- Non-critical PK samples collected outside of the protocol-defined window: Actual times will be used for PK parameter calculation. If a chronic pattern of deviation is noted, it will be evaluated individually and discussed at the BDRM.
- Non-critical PK samples not collected: Missing data will be treated as missing data and no parameters will be excluded unless the missing data impact the objective acceptance criteria for elimination rate related parameters.
- Sample processing errors that might render a subject's bioanalytical data to be inaccurate: Data affected by these errors will be evaluated during PK parameter analysis to determine whether or not they can be included in the PK analysis. If warranted, this may be discussed during the BDRM

An additional statistical analysis will be performed excluding subjects with major GCP violations (i.e. GCP violations observed at site 10703) (see Section **Error! Reference source not found.**).

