### 13.2. PHARMACOKINETIC PARAMETERS

For PK parameter calculations following the first dose, predose samples that are BLQ or missing will be assigned a numerical value of zero. Any anomalous concentration values observed at predose will be identified in the study report and used for the computation of PK parameters. Pharmacokinetic parameters will be computed if the anomalous concentration is not greater than 5% of the observed maximum concentration ( $C_{max}$ ). If the anomalous concentration is greater than 5% of  $C_{max}$ , the PK parameters for the given subject will be calculated and reported in the listing, but excluded from statistical summaries and analyses. For the second dose, a predose sample that is BLQ will be assigned a numerical value of zero. Missing predose samples will be set to missing.

Any other BLQ concentrations will be assigned a value of zero if they precede quantifiable samples in the initial portion of the profile. A BLQ value that occurs between quantifiable data points prior to  $C_{max}$  will be set to missing. Following  $C_{max}$ , BLQ values embedded between 2 quantifiable data points will be treated as missing when calculating PK parameters. If a BLQ value occurs at the end of the collection interval (after the last quantifiable concentration), it will be set to zero. If consecutive BLQ concentrations are followed by quantifiable concentrations in the terminal portion of the concentration curve, these quantified values will be excluded from

---

Document:	\\ieedc-vnasc01\Biosdata\Archigen\SAIT101\YWA21301\Biostatistics\Documentation\SAP		
Author:		Version Number:	V2.0
		Version Date:	13Feb2019

Template No: CS\_TP\_BS016 Revision 4  
Effective Date: 01Apr2016

Reference: CS\_WI\_BS005

the PK analysis by setting them to missing, unless otherwise warranted by the concentration-time profile.

Subjects with partial data will be evaluated on a case-by-case basis to determine if sufficient data are available for reliable estimation of PK parameters.

The following PK parameters will be estimated for SAIT101, MabThera® and Rituxan® by noncompartmental methods using actual elapsed time, where possible.

$AUC_{(0-t)}$	Area under the serum concentration-time curve from time zero (immediately predose on Day 1) to time of last quantifiable concentration ( $\mu\text{g}\cdot\text{h}/\text{mL}$ ), calculated by linear up/log down trapezoidal summation.

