$AUC_{(0-\text{inf})}$	Area under the serum concentration-time curve from zero (immediately predose on Day 1) extrapolated to infinite time ( $\mu\text{g}\cdot\text{h}/\text{mL}$ ), calculated by linear up/log down trapezoidal summation and extrapolated to infinity by addition of the last quantifiable concentration divided by the elimination rate constant: $AUC_{(0-\text{last})} + C_{\text{last}}/\lambda_z$ . For presenting data purpose, symbol $AUC_{(0-\text{inf})}$ instead of $AUC_{(0-\infty)}$ will be used in all PK analysis and reporting.
$AUC_{(0-d15)}$	Area under the serum concentration-time curve from zero (immediately predose on Day 1) until Day 15 prior to infusion ( $\mu\text{g}\cdot\text{h}/\text{mL}$ ), calculated by linear up/log down trapezoidal summation.  Actual time/concentration on Day 15 will be used for the calculation of this parameter unless the parameter is derived by interpolation (see below); 

• A window of 312 to 360 hours postdose for the 336-hour (Day 15) time point (which has been selected as a window that would not create an influence of more than <math>\pm 5\%</math> on the AUC) will be used as an acceptance criterion, for calculation using actual time/concentration on Day 15, and for inclusion of this parameter in descriptive and inferential statistics;

• If the 336-hour sample was collected after 360 hours (i.e., outside the defined time window) but prior to the second dose, then a log-linear interpolation will be used to derive the concentration at 336 hours for computation of <math>AUC_{(0-d15)}</math>;

• If the 336-hour sample is missing or was collected before 312 hours, the <math>AUC_{(0-d15)}</math> will be set to missing.

$AUC_{(w2-w24)}$	Area under the serum concentration-time curve from Week 2 (predose) to Week 24 ( $\mu\text{g}\cdot\text{h}/\text{mL}$ ), calculated by linear up/log down trapezoidal summation.
$AUC_{(0-w12)}$	Area under the serum concentration-time curve from zero (predose) to Week 12 ( $\mu\text{g}\cdot\text{h}/\text{mL}$ ), calculated by linear up/log down trapezoidal summation.

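### A missing Day 15 predose sample is not negligible for AUC(0-t) and AUC(0-inf): the SAP's trapezoid rule then overstates both by about 7-15% in each affected patient, although the arm-level effect is probably small

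*SAP*

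**What the plan says.** SAP section 13, under the 336-hour bullet, covers two events in one rule: "if this sample is missing or collected outside of a window of 312 to 360 hours postdose for the 336-hour time point". In either event Ctrough is not evaluable, but the impact on AUC(0-inf), the parameters related to it and AUC(0-last) "is considered negligible and those parameters will generally not be excluded from descriptive and/or inferential statistics".

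SAP section 13.2 then fixes how the AUC is computed. For the second dose, "Missing predose samples will be set to missing". AUC(0-t) and AUC(0-inf) both start at Day 1 predose and are "calculated by linear up/log down trapezoidal summation", with the usual extrapolated tail for AUC(0-inf).

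Three other rules bear on the point:

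- **AUC(0-d15), same sample.** SAP 13.2 has a rule that opens "If the 336-hour sample is missing or was collected before 312 hours, the" and goes on to set AUC(0-d15) to missing.
- **Tolerance.** The 312-360 h window for AUC(0-d15) is one "which has been selected as a window that would not create an influence of more than" ±5% on the AUC.
- **End-of-infusion samples.** If both the end-of-infusion and the 1 h post-infusion samples are missing, SAP 13 makes AUC not evaluable.

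AUC(0-t) and AUC(0-inf) are two of the five co-primary endpoints.

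**The concern.** SAP 13 justifies its tolerance in the bullet on doses given outside the window: with a long half-life and long sampling, shifts in sampling time matter little. The 336-hour bullet carries that conclusion over to a sample that does not exist, where the reasoning no longer applies.

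Protocol Table 2, footnote s, schedules no sample between Day 8 (168 h) and Day 15 predose. Without the predose value, the next point after Day 8 is 3 h into the second infusion. By Table 1, 900 of the 1,000 mg has been given by then (50 + 100 + 150 mg in 90 minutes, then 400 mg/h for 90 minutes = 600 mg). The concentration there is higher than on Day 8, so the segment counts as rising and is joined by a straight line. The true concentration falls for 7 days and jumps only when the infusion starts.

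At stake is the validity of individual co-primary values entering the equivalence ANOVA. AUC(0-w12) is inflated too, and CL and VD, which divide by AUC(0-inf), are understated. If the missing samples fall unequally across arms, the ratio shifts.

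**Working it through.** **Inputs.**

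- Protocol 1.3.1: CL 221-242 mL/day, steady-state volume 4.28-4.74 L, terminal half-life 19-22 days.
- Protocol Table 1: infusion steps, 1,000 mg per infusion.
- Protocol Table 2, footnote s: sampling times.
- Assumed: a central volume of 2.5-4.0 L for the two-compartment model, because the documents give only the steady-state volume.

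**Method.** Superpose the stepped infusions, sample on the protocol schedule, integrate by linear-up/log-down, then delete the 336 h point and integrate again.

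**Step 1. The SAP's own figure.** Moving the 336 h sample to 312 h or 360 h changes AUC(0-d15) by -5.2% to +5.0% (one compartment) and by no more than -4.9% to +4.6% (two compartments). The stated ±5% reproduces.

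**Step 2. One patient by hand** (one compartment, CL 0.23 L/day, V 4.5 L). Concentrations: Day 8, 156; Day 15 predose, 109; 3 h into infusion 2, 308 µg/mL.

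- With the predose point: log-down segment (156 - 109)/ln(156/109) × 7 = 918, plus linear segment (109 + 308)/2 × 0.125 = 26. Total 944 µg·day/mL.
- Without it: (156 + 308)/2 × 7.125 = 1,653 µg·day/mL.
- Excess: 1,653 - 944 = 709. On a full AUC(0-t) of about 8,700, that is +8.1%.

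**Step 3. Range per affected patient.**

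| Model | AUC(0-t), AUC(0-inf) |
|---|---|
| One compartment, protocol CL and volume | +7.4% to +9.0% |
| Two compartments, protocol CL, volume and half-life, assumed central volume | +8.7% to +15.1% |
| One compartment forced to a 19-22 day half-life (volume 6.1-7.7 L, outside the protocol's range) | +5.0% to +5.8% |

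In the first two models AUC(0-w12) rises by +7.6% to +15.7%. CL changes by 1/(1 + e) - 1, where e is the proportional error in AUC(0-inf): -6.9% at e = 0.074 and -13.1% at e = 0.151.

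**Step 4. Mistimed sample, for contrast.** A sample at 288 h, used at its actual time with the infusion still at 336 h, raises AUC(0-t) by only about +2% to +4%.

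**Step 5. Missing end-of-infusion pair, for contrast.** Losing both samples around the end of one infusion changes AUC(0-t) by about -0.2% to -2.0% in these models. The SAP voids AUC for that smaller error.

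**Step 6. Arm level.** If k of n patients in an arm are affected, its geometric mean is multiplied by (1 + e)^(k/n). With k = 3 and n = 84 (an assumed count; the documents give no rate), the shift is 0.24% at e = 0.07, 0.37% at e = 0.11 and 0.50% at e = 0.15.

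**Step 7. Could the conclusion change?** The log-scale SD is √ln(1 + CV²), and the 90% CI half-width is 1.65 × SD × √(2/84).

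- CV 33%: SD 0.322, half-width 0.082, leaving 0.223 - 0.082 = 0.141 to ln 1.25.
- CV 37.3% (the protocol's figure for AUC(0-inf)): SD 0.361, half-width 0.092, leaving 0.131.

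Since ln 1.15 = 0.140, at CV 37.3% and a true ratio of 1 about 0.131/0.140 = 94% of one arm, and none of the other, would need a +15% error before the interval reached 1.25. At a true ratio of 1.10 (ln = 0.095), the share is (0.131 - 0.095)/0.140, about 26%.

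**Step 8. The extrapolation fix.** Carrying each patient's 48 h to Day 8 log-linear slope forward to 336 h leaves an error of 0% (one compartment) to about -1.3% (two compartments).

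**The case against.** The strongest reply is that the plan has ways to catch such a profile. The retention rule is qualified by the word generally, SAP 13.2 provides case-by-case evaluation of subjects with partial data, and SAP section 4 sets up a blinded review of PK/PD data before PK set allocation is final. This stands in part. These provisions permit exclusion but do not require it, while the one rule specific to this sample points to retention.

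A missing sample is also likely to be uncommon. Patients in the PK set received the second infusion, so they attended; a predose immunogenicity sample is taken at that visit (Table 2, footnote t); and serum is kept in duplicate (protocol 3.6.3.1). That stands, and it limits the practical weight of the point.

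The range depends on the model. The one-compartment figures imply a half-life of 12-15 days rather than the protocol's 19-22, and the top of the range rests on an assumed central volume. The direction is secure; the exact percentage is not. The ±5% tolerance was set for a timing window on AUC(0-d15), so it is a yardstick here and not a limit the SAP imposes on AUC(0-t).

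A reader might infer that both co-primary endpoints, or their ratios, are biased by 7-15%. The documents do not support that: the figure is per affected patient, equal missingness across arms largely cancels, and no missingness rate is given. Nor do the calculations support a charge against mistimed samples, where the SAP's position is defensible.

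**Conclusion.** The point holds for missing samples only. Followed as written, SAP 13 and 13.2 produce an AUC(0-t) and AUC(0-inf) about 7-15% too high in any patient whose Day 15 predose sample is missing. The lower part of that range (7-9%) needs only the protocol's CL and volume; the upper part needs an assumed central volume of 2.5-4.0 L. AUC(0-w12) is overstated, and CL and VD understated, by the same mechanism. The SAP is also inconsistent with itself, since it voids AUC(0-d15) for the same missing sample and voids AUC when both end-of-infusion samples are missing.

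The effect on the geometric mean ratio is small unless missingness is frequent and unequal between arms, and a changed equivalence conclusion is unlikely. The case for acting is that a co-primary value known to be wrong should not depend on a discretionary review for its removal.

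**What to change.** In SAP 13, confine the negligible-impact statement to a 336 h sample that was collected off schedule and is used at its actual time. Do not extend the new rule to samples drawn before 312 h.

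For a missing Day 15 predose sample, pre-specify one of two rules in SAP 13 and 13.2, with the other as a sensitivity analysis:

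1. Declare AUC(0-t), AUC(0-inf), AUC(0-w12), CL and VD not evaluable. This is the simpler choice and matches the SAP's existing treatment of AUC(0-d15) and of missing end-of-infusion samples.
2. Extrapolate log-linearly from that patient's 48 h and Day 8 samples to the actual start of the second infusion, and use the value only for those parameters. The small residual error in step 8 comes from noise-free profiles and would be larger with real data. SAP 6.3 defaults to no imputation, so this exception would have to be stated.

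Under either rule, Ctrough and AUC(0-d15) stay as the SAP now handles them. The cost is a change of wording, a few values lost or imputed, and one extra step before the noncompartmental run.
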